**4) Number of Subjects\***

The study population will be comprised of 75 patients assigned to one of three groups of 25 COVID (+) patients each.

The proportion of subjects with AT3 levels < 100% will be 50/50 randomization of which 25 subjects with AT3 <100% will be standard of care and 25 subjects with AT3<100% will be standard of care with exogenous AT3 supplementation. The third group will be subjects with AT3 levels  $\geq 100\%$ .

- a. 25 patients with endogenous AT3 >100% who receive standard of care only or
- b. 25 patients with endogenous AT3 <100% who receive standard of care only or
- c. 25 patients with endogenous AT3 <100% who receive standard of care plus supplemental AT3.

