**7) Study Endpoints\***

The Primary endpoint is change from baseline in the ISTH DIC Score to Day 9.

The Secondary endpoints include change from baseline D-dimers, Fibrinogen & Prothrombin time, length of hospital stay (days), mortality (%), and Pulmonary function (including Time (days) to mechanical ventilation and/or ECMO Duration (days) of new ventilator or extracorporeal membrane oxygenation (ECMO) use, Change from baseline SOFA and SOFA Respiratory sub-score, Number of venous thromboembolisms, Number of major bleeding events

Subjects discharged prior to completion of intervention would be classified as having a successful outcome. We anticipate that all cause morbidity will occur in 10-20% of the COVID study population, despite standard of care. We anticipate that these patients will be deficient in endogenous AT3.

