**8) Procedures Involved\***

Any member of the study team will discuss potential subjects with the clinical team for appropriate pursuit of informed consent and screening for eligibility.

75 eligible subjects, after consent, will have laboratory blood tests for further screening.

25 of those subjects with endogenous **AT3  $\geq$  100%** will continue with SOC.

50 of those subjects with endogenous **AT3 < 100%** will be will be randomly assigned to begin **SOC plus treatment with exogenous AT3 supplementation or only SOC** treatment. The randomization schedule will be established by a member of the study team that is not involved in the informed consent process.

They will all be followed up for laboratory blood tests, study endpoints and adverse events. If they do not meet entry criteria they will be excluded from the study.

[figure not shown]
Consented subjects will be scored according to The International Society of Thrombosis and Haemostasis Disseminated Intravascular Coagulation scale (ISTH DIC) on study visit days 1, 3, 5, 7, 9 and 11.

The SOFA score will be performed only when the parameter is obtained clinically and monitored for changes in patient status on study visit days 1, 3, 5, 7, 9 and 11. Each organ system is assigned a point value from 0 (normal) to 4 (high degree of dysfunction/failure). It will be calculated on admission and Day 11 using the worst parameters measured during the study visit day. If a parameter is not obtained clinically it will be voided for research purposes.

UM IRB# 20201048

AT3 in COVID-19  
January 24, 2022, Version 6.2

After enrollment and each 48h period (+/- 12 hours) thereafter, blood samples are collected and assayed for routine clinical coagulation and inflammation markers, including AT3 activity, D-Dimer, anti-Xa, fibrinogen, and prothrombin time until Day 11.

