## **9) Statistics\***

Statistical analyses will be performed using SPSS version 21 (IBM Corporation, Armonk, NY). Parametric data are reported as  $M \pm SD$  and nonparametric data are reported as median (interquartile range). Missing values for continuous variables are handled by applying imputation methods before calculating their statistics. The study population will be stratified into two halves based on the primary outcome of change from baseline SOFA and/or ICH DC. Those with the fastest rate of recovery are compared to those with the slowest rate of recovery. We expect that AT3 will correlate with rate of recovery and/or with one or more of the secondary outcomes. The demographics and physiologic variables in the fastest and slowest groups are compared using a t test or Mann-Whitney U-test, as appropriate. Categorical variables are compared using a  $\chi^2$  or Fisher's exact test, as appropriate. Statistical significance is determined at  $p < 0.05$ . Then multivariate models will be evaluated for predicting the primary or secondary outcomes, using various performance metrics, such as area under the receiver operating characteristic curve, sensitivity and specificity, positive predictive value, and negative predictive value, as we have described in multiple previous studies. In addition, propensity scores will be assigned for each patient based on a 1:1 fixed ratio nearest neighbor matching was performed to compare those with fastest or slowest recovery. A 1:1 fixed ratio nearest neighbor matching is performed to minimize bias without sacrificing power, as we have described in multiple previous studies.

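### ISTH DIC is scored at five post-baseline visits, but only Day 9 feeds an endpoint, and Section 9 names neither a repeated-measures model nor a comparison of the randomised arms

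*Combined protocol and SAP*

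**What the plan says.** Section 7 sets the primary endpoint: "The Primary endpoint is change from baseline in the ISTH DIC Score to Day 9". Appendix C likewise takes the D-dimer, fibrinogen and prothrombin time changes to Day 9 only.

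Section 8 scores all consented subjects more often ("ISTH DIC) on study visit days 1, 3, 5, 7, 9 and 11"), and the Appendix B flowsheet agrees. That gives one baseline and five post-baseline readings, four of them up to Day 9.

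Section 4 gives the size: "The study population will be comprised of 75 patients assigned to one of three groups of 25 COVID (+) patients each". Only the two groups with AT3 below 100% are randomised, so the randomised comparison is 25 v 25.

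Section 9 uses the outcome to form groups: "The study population will be stratified into two halves based on the primary outcome of change from baseline SOFA and/or ICH DC". It continues: "Those with the fastest rate of recovery are compared to those with the slowest rate of recovery". Rate of recovery is not defined. No longitudinal model, visit average or area under the curve is named, and no test of one randomised arm against the other. Appendix C mentions a between-group result for mortality alone.

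On missing data, Section 9 says: "Missing values for continuous variables are handled by applying imputation methods before calculating their statistics". No method is given. Section 7 adds a rule for patients who leave early: "Subjects discharged prior to completion of intervention would be classified as having a successful outcome".

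**The concern.** The randomised comparison is small, and the score is a coarse integer from 0 to 8 (Appendix A maxima: 2 for platelets, 1 for fibrinogen, 2 for prothrombin time, 3 for D-dimer). All the information on the primary endpoint is placed on one visit. The patients are inpatients, so that visit is exposed to discharge and death.

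Two things are at stake. First, a patient who leaves between Days 7 and 9 may have three observed post-baseline scores, and the plan does not say that these will be used when the Day 9 score is missing. Second, if an effect appears early and the standard-of-care arm has caught up by Day 9, no stated endpoint based on this score or its laboratory components can show it.

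**Working it through.** **Inputs from the documents.** Visits on Days 1, 3, 5, 7, 9 and 11 (Section 8, Appendix B); 25 per randomised arm (Section 4); significance at p < 0.05 (Section 9; two-sided assumed).

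**Inputs assumed.** The documents give no SD, between-visit correlation, effect size, power or dropout, so there is no plan figure to reproduce. I take equal variance (1 unit) at each visit and adjacent-visit correlation r from 0.5 to 0.8. The covariance is compound symmetry, AR(1), or a 50:50 mix. The effect is 0.5 SD of the raw score at Day 9.

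**Step 1: Day 9 contrast, complete data.** Per-patient variance adjusted for baseline is 1 − ρ², where ρ is the correlation between Day 1 and Day 9. If everyone has every visit, a model with unstructured covariance and baseline-by-visit terms gives the same Day 9 estimate as analysis of covariance at Day 9 alone. The extra visits gain essentially nothing.

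Baseline adjustment is a separate gain that needs no extra visit. Under compound symmetry the raw change has variance 2(1 − r), against 1 − r² adjusted: 1.00 v 0.75 at r = 0.5, and 0.60 v 0.51 at r = 0.7.

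**Step 2: Day 9 contrast with loss.** Assume 10% leave after each of Days 3, 5 and 7, so 30% have no Day 9 score, and that the loss is ignorable. Complete cases give variance v9/0.7. The mixed model's variance is the Day 9 element of the inverse of the summed information, Σ pₘ·Cₘ⁻¹, with Cₘ the baseline-conditional covariance of the first m post-baseline visits. The ratio of mixed model to complete cases is 0.89 to 0.96, a saving of 4-11%.

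**Step 3: the Day 3-9 average, a different estimand.** Under compound symmetry its baseline-adjusted variance is (1 − r)(1 + 4r)/4. The AR(1) rows come from conditioning the five-visit matrix on baseline. Power uses variance (2/25)·v and a constant 0.5 SD effect from Day 3.

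| Structure, r | Day 9 variance | Average variance | Ratio | Power, Day 9 | Power, average |
|---|---|---|---|---|---|
| Compound symmetry, 0.5 | 0.750 | 0.375 | 0.50 | 53% | 82% |
| Compound symmetry, 0.7 | 0.510 | 0.285 | 0.56 | 70% | 91% |
| Compound symmetry, 0.8 | 0.360 | 0.210 | 0.58 | 84% | 97% |
| AR(1), 0.5 | 0.996 | 0.461 | 0.46 | 43% | 74% |
| AR(1), 0.8 | 0.832 | 0.425 | 0.51 | 49% | 77% |

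Over all three structures the ratio is 0.46-0.58, and power is 43-84% for Day 9 against 72-97% for the average.

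**Step 4: other effect shapes.** The average is the more efficient only if the mean effect exceeds √ratio of the Day 9 effect: √0.46 = 0.68 to √0.58 = 0.76.

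- Linear build (25, 50, 75, 100% of the Day 9 effect): the mean is 0.625 of the Day 9 effect. Relative efficiency is 0.625²/ratio, or 0.67 to 0.84. The average is worse throughout.
- Effect at Day 9 only: the mean effect is 0.5/4 = 0.125 SD. Power falls from 43-84% to 10-16%. For example, under compound symmetry with r = 0.8, 0.125/√(0.08 × 0.21) = 0.96, which gives 16%.

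**The case against.** A reader might infer that the primary endpoint carries about twice the variance that the collected data allow. The documents do not support that. The twofold figure (Step 3) sets the Day 9 effect against an average over four visits. It does not carry over to the Day 9 contrast, where the saving is nil with complete data and 4-11% under an assumed 30% loss. It also rests on correlations the documents do not give and on a constant effect from Day 3. Section 8 schedules dosing on Days 1, 3, 5, 7 and 9, subject to AT3 level, so an effect that builds is at least as plausible, and then the average does worse.

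A reader might also infer that the interim scores are discarded. The plan is silent rather than explicit. The undefined rate of recovery or the unnamed imputation could draw on them, and the component tests also serve coagulation monitoring (Section 13).

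Three further objections stand in part:

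- This is a self-described pilot with no power claim, and the lack of any arm comparison in Section 9 matters more than the choice between a mixed model and Day 9 analysis of covariance. That is fair, but the same edit supplies both.
- A mixed model treats missing scores as ignorable, which conflicts with counting early discharge as success. This stands in full and shapes the fix.
- Equal-variance normal theory is rough for this score. In the 24-patient cohort described in Section 2, platelets, prothrombin time and fibrinogen would mostly score zero, leaving D-dimer to drive the total. The power figures are illustrative.

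**Conclusion.** The point holds as a gap in specification. Four of the five post-baseline ISTH DIC readings (Days 3, 5, 7 and 11) have no stated use, and Section 9 names neither a repeated-measures analysis nor a comparison of the randomised arms.

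For the primary Day 9 contrast the benefit of using the interim visits is modest: none with complete data, and about 4-11% lower variance if 30% lack Day 9 and the loss is ignorable (both assumed). For the average effect, the variance of about 46-58% of baseline-adjusted Day 9 is worthwhile only if the effect is roughly constant from Day 3. Because the average can lose efficiency or most of its power under other shapes, it belongs among the secondary results. None of this shows that Day 9 is the wrong primary time point.

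**What to change.** In Section 9:

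1. Compare the two randomised AT3 <100% groups with one mixed model for repeated measures on ISTH DIC at Days 3, 5, 7 and 9. Terms: arm, visit, arm-by-visit, baseline score and baseline-by-visit.
2. Keep the Day 9 contrast from this model as the primary estimate. Add the average Day 3-9 contrast as a prespecified secondary result.
3. Reconcile the model with Section 7's early-discharge rule. Say what counts as completing the intervention in the arm that receives no infusion, and how a success enters an analysis of a numeric score. State how death before Day 9 is handled.
4. Add one sensitivity analysis that does not treat these missing scores as ignorable. One option is a rank comparison of the arms at Day 9, with deaths placed worst and early live discharges placed best. The Mann-Whitney test it needs is already named in Section 9, and ranks also suit the coarse score.
5. Say what the Day 11 score is for, even if only description.

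This needs no new visits, samples or patients. The cost is revised wording, one more secondary estimate and one sensitivity analysis.

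### Section 9 specifies no between-arm analysis of the primary endpoint and no baseline adjustment, although the Day 1 score is collected in everyone and adjusting for it would improve precision at almost no cost

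*Combined protocol and SAP*

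**What the plan says.** Section 7 defines the primary endpoint: "The Primary endpoint is change from baseline in the ISTH DIC Score to Day 9". Section 7 and Appendix C define D-dimer, fibrinogen, prothrombin time and SOFA as changes from baseline too.

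Section 4 sets the size: "The study population will be comprised of 75 patients assigned to one of three groups of 25 COVID (+) patients each". Only patients with AT3 below 100% are randomised: "25 subjects with AT3 <100% will be standard of care and 25 subjects with AT3<100% will be standard of care with exogenous AT3 supplementation". Those with higher AT3 form a separate group of 25 and are not randomised.

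Section 8 schedules the ISTH DIC score "on study visit days 1, 3, 5, 7, 9 and 11", and the Appendix B flowsheet lists both that score and the AT3 level at Day 1 for all subjects.

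Section 9 uses the primary outcome to divide the whole study population into two halves by speed of recovery. The tests it names for continuous data apply to those halves: "The demographics and physiologic variables in the fastest and slowest groups are compared using a t test or Mann-Whitney U-test, as appropriate". The multivariate models that follow are for prediction and are judged by ROC area, sensitivity, specificity and predictive values; no covariate and no treatment term is named. The propensity matching also contrasts fast with slow recoverers. The expectation stated about antithrombin is "We expect that AT3 will correlate with rate of recovery and/or with one or more of the secondary outcomes". The significance threshold is p < 0.05, with sidedness not given.

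**The concern.** The trial has one randomised contrast, and it is small. The statistics section never says how the primary endpoint will be compared across it. An analyst who fills the gap by default would probably apply an unadjusted two-sample test to the change scores. That would be valid, but it would discard information that the trial already collects.

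A change score fixes the coefficient on the baseline value at 1. When the correlation between baseline and Day 9 is below 1 and the SDs are similar, that coefficient is too large, and baseline variation adds noise to the arm difference. A model that estimates the coefficient removes that noise. With 25 patients per arm the difference could matter.

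Leaving the analysis unstated also means that the choice between adjusted and unadjusted could be made after the data are seen.

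**Working it through.** **1. What the documents supply.** 25 patients per randomised arm (Section 4); p < 0.05 (Section 9), taken here as two-sided; a Day 1 ISTH DIC score in everyone (Section 8, Appendix B). There is no power or sample-size statement to reproduce. The SD of the change, the effect size and the baseline-to-Day 9 correlation ρ are absent. ρ is therefore assumed to lie between 0.3 and 0.8, and effects δ between 0.3 and 1.0 SD of the change.

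**2. Variance.** Let the score have the same SD σ on Day 1 and Day 9.

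- Change score: 2σ²(1 − ρ)
- Linear model adjusted for baseline: σ²(1 − ρ²)
- Ratio, adjusted to change: (1 − ρ²) / [2(1 − ρ)] = (1 + ρ)/2
- Proportional cut: 1 − (1 + ρ)/2 = (1 − ρ)/2

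| ρ | 0.3 | 0.4 | 0.5 | 0.6 | 0.7 | 0.8 |
|---|---|---|---|---|---|---|
| Variance cut | 35% | 30% | 25% | 20% | 15% | 10% |

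**3. Power.** By the normal approximation, unadjusted power is Φ(δ/√(2/25) − 1.96), with √(2/25) = 0.283. For the adjusted analysis, divide δ by √((1 + ρ)/2), which is 0.866 at ρ = 0.5.

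Example, δ = 0.6. Unadjusted: 0.6/0.283 − 1.96 = 0.16, power 56.4%. Adjusted: 0.6/(0.283 × 0.866) − 1.96 = 0.49, power 68.8%. Gain 12.4 points.

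| δ (SD of change) | Unadjusted | Adjusted, ρ = 0.5 | Gain (points) |
|---|---|---|---|
| 0.3 | 18% | 23% | 5 |
| 0.4 | 29% | 37% | 8 |
| 0.5 | 42% | 53% | 11 |
| 0.6 | 56% | 69% | 12 |
| 0.7 | 70% | 82% | 12 |
| 0.793 | 80% | 90% | 10 |
| 0.9 | 89% | 96% | 7 |
| 1.0 | 94% | 98% | 4 |

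At δ = 0.6 the gain is 18.5 points for ρ = 0.3 and 4.5 points for ρ = 0.8. Over the whole grid it runs from about 1.6 to 18.5 points. Noncentral t calculations (48 and 47 degrees of freedom) give gains within about 1 point of these.

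**4. Coarse scale.** Under Appendix A the score is an integer from 0 to 8 (maxima 2 + 1 + 2 + 3), so step 3 is approximate. As a limited check, 3,000 trials were simulated with the D-dimer item alone (0/2/3). Assumptions: log D-dimer normal with SD 0.8, median 3 times ULN, latent ρ = 0.5, effect 0.8 latent SD. Power was 59% for t on change, 58% for Mann-Whitney and 74% for the baseline-adjusted model. Rejection under the null was close to 5% for each. With a median of 8 times ULN the gain over the t test was only about 6 points. The direction survives coarse scoring; the size depends on where patients sit on the scale.

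**5. Outcome on Day 9 or on change.** With the Day 1 score in a linear model, taking the Day 9 score or the change as the outcome gives the same arm coefficient. The Section 7 endpoint can stand unaltered.

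**The case against.** A reader might infer that the plan tests the primary endpoint between arms with an unadjusted t or Mann-Whitney test, since those are the only tests it names for continuous data. The text does not support that. They compare demographic and physiologic variables between halves defined by outcome. The unadjusted power above therefore belongs to a natural default, which the plan itself does not state. The missing randomised comparison is the larger gap, and adjustment is part of how to fill it.

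It is also tempting to say that a change score biases the treatment estimate. Under randomisation it does not, and the simulated type I error was about 5% for every method. A typical chance baseline imbalance at 25 per arm is 0.283 SD, which moves the change contrast by 0.283 × (1 − 0.5) = 0.14 SD at ρ = 0.5. That is ordinary sampling variation already counted in the variance ratio, so it is not a further loss. Nor does a linear model cure the floor at a score of 0.

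Section 9's expectation about AT3 might be read as grounds for crediting baseline AT3 with part of the gain. The sentence does not say baseline AT3, its range is restricted to below 100% in the randomised patients, and the documents offer nothing to quantify its value.

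Finally, this is a self-described pilot with no power target, so no promised figure is missed. That limits the severity. It is no reason to leave the one randomised contrast unspecified.

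**Conclusion.** The point holds as an omission in Section 9. The primary endpoint has no specified comparison between the randomised arms and no baseline adjustment, although the Day 1 score is collected in everyone.

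The size of the gain is conditional. A variance cut of 25% requires ρ = 0.5, and a gain of 10 to 12 points requires in addition that unadjusted power be roughly 40–80%. Neither is a fact about this trial. The supportable statement is a 35% to 10% cut for ρ from 0.3 to 0.8 and about 2 to 18 points of power over the grid examined. It assumes equal SDs at the two times, an approximately linear relation and all 50 randomised patients analysed. The last may fail: Section 7 classes early discharges as successes without giving them a Day 9 score, and Section 9 does not say which imputation method applies.

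The benefit is precision. None of it is attributed to AT3. The change should be made, but its absence does not make the trial invalid.

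**What to change.** Add to Section 9:

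- The primary analysis compares the two randomised arms, as assigned (25 versus 25), by a linear model of Day 9 ISTH DIC score, or equivalently its change, on arm and Day 1 score. Day 1 AT3 may be a second covariate if that is decided in advance. Report the adjusted difference with a 95% CI.
- A proportional-odds model of the Day 9 score with the same covariates is a sensitivity analysis, because the scale is coarse.
- D-dimer (log scale), fibrinogen and prothrombin time are analysed in the same form, each with its own baseline.
- State how patients discharged before Day 9 enter the model. The label of success is not a score, and the model cannot be run on all 50 patients without such a rule.

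Apply the same form to SOFA only after its schedule is reconciled. Appendix C defines change to Day 9. Appendix B schedules SOFA at Day 1 and Day 11 only. Section 8 lists Day 9 among the monitoring days but calculates the score on admission and Day 11.

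For ISTH DIC and the three laboratory endpoints the cost is wording: no added patients or measurements, and one or two degrees of freedom.

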Thus, COVID might be a dysregulated inflammatory state superimposed on disseminated intravascular coagulation (DIC) with consumptive coagulopathy [PMID: 32302438]. These patients are at high risk for both thrombosis and bleeding, as well as an overwhelming cytokine storm. The pathogenic mechanism is not fully elucidated, but the dysregulated coagulation is probably orchestrated by inflammatory cytokines, lymphocyte cell-death, hypoxia, and endothelial damage [PMID: 32558075]. This is a project to develop an entirely novel evidence-based treatment that targets both the coagulopathy and the inflammation.

In 183 consecutive patients with COVID, the overall mortality was 11.5%. On admission, the non-survivors had higher D-dimer and fibrin degradation product (FDP) levels, longer prothrombin time and activated partial thromboplastin time compared to survivors; 71.4% of the deaths and only 0.6% survivors met the criteria of DIC [PMID: 32073213]

In 40 patients with COVID, whole blood thromboelastometry (TEM) was consistent with hypercoagulability characterized by an acceleration of blood clot formation and higher clot strength. This hypercoagulable state persists for at least 5-10 days and was associated with deep vein thrombosis in six patients (15%), thromboembolism in 2 patients (5%), and catheter-related thrombosis in 12 patients (30%). The ICU and the hospital mortality were 10% and 12.5%, respectively. [PMID: 32394236]

In 16 COVID patients, the pro-coagulant TEM profile was characterized by an increased clot strength (CS), platelet contribution to CS, fibrinogen contribution to CS elevated D-dimer levels, and hyperfibrinogenemia. Fibrinogen levels were associated with interleukin-6 values. [PMID: 32302448].

In 24 COVID patients, the R, K, Alpha, and MA TEM parameters were all consistent with hypercoagulability. Platelet count was normal or increased, prothrombin time and activated partial thromboplastin time were near normal. Fibrinogen, D-dimer, C-reactive protein, Factor VIII and von Willebrand factor, protein C were all increased whereas AT3 was decreased [PMID: 32302438]. In 94 patients with COVID vs 40 healthy controls, whereas D-dimer, fibrin/fibrinogen degradation products (FDP), and fibrinogen (FIB) in all SARS-CoV-2 cases were all higher, but AT3 was lower [PMID: 32172226].

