**13) Risks to Subjects\***

Hypersensitivity reactions, including anaphylaxis, are possible. Should symptoms occur, THROMBATE III infusion will be discontinued and appropriate treatment begun as per clinical judgement.

- Because THROMBATE III is made from human blood, it may carry a risk of transmitting infectious agents, e.g., viruses, the variant Creutzfeldt-Jakob disease (vCJD) agent and, theoretically, the Creutzfeldt-Jakob disease (CJD) agent.
- We will perform coagulation tests to avoid excessive or insufficient anticoagulation and monitor for bleeding or thrombosis. Assessment will be based on clinical findings at the discretion of the treating physician along with laboratory values of PT, PTT, Hemoglobin and Hematocrit analysis. Treatment may include heparin for excessive coagulation or blood transfusion for insufficient coagulation ultimately left to the discretion of the treating physician.

Two clinical trials were conducted in 33 subjects with congenital AT deficiency. Nine subjects (27%) experienced 29 adverse reactions which occurred during 17 of 389 infusions. There were no serious adverse reactions reported. The severity of adverse reactions was reported as mild or moderate, except for wound secretion and hematoma, which was severe.

Dizziness (12%), Chest discomfort (9%), Nausea (9%), Dysgeusia (6%), Pain (cramps) (6%), and each of the following were reported in 3% of the subjects: Chills, Wound secretion and hematoma, Vision blurred, Chest pain, Dyspnea, Intestinal dilatation, Pyrexia and Urticaria,

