**Appendix A**

**ISTH DIC**, the score is increased by 2 points for abnormal baseline D-dimers (fibrin-related marker) and/or abnormal fibrinogen <1.0 gram/L level (1 point). This scoring algorithm was developed by the ISTH Scientific and Standardization Committee (SSC) committee on DIC and published in 2001. The ISTH DIC is a set of objective criteria for the diagnosis and severity of DIC with a score of  $\geq 5$  correlating with overt DIC, whereas < 5 does not rule out DIC but may indicate DIC that is not overt. The score is only appropriate for use in patients with an underlying disorder that is known to be associated with DIC; e.g., sepsis, severe immunological reactions, etc.

The ISTH DIC score is calculated using

- platelet count ( $\geq 100,000 = 0$ ;  $50,000-99,999 = 1$ ;  $< 50,000 = 2$ ),
- fibrinogen level ( $\geq 100 \text{ mg/dL} = 0$ ;  $< 100 \text{ mg/dL} = 1$ ),
- prothrombin time prolongation above upper limit of normal (ULN)
  - ( $< 3 \text{ seconds} = 0$ ,  $3-6 \text{ seconds} = 1$ ,  $> 6 \text{ seconds} = 2$ ),
- and D-dimer ( $< 2 \text{ times ULN} = 0$ ,  $2-4 \text{ times ULN} = 2$ ,  $> 4 \text{ times ULN} = 3$ ).

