### Appendix C

The Secondary endpoint measurements:

- a. D-dimer level change from baseline to Day 9 in mcg/mL FEU or DDU,
- b. Fibrinogen level change from baseline to Day 9 in mg/dL
- c. Prothrombin time change from baseline to Day 9 in seconds
- d. Length of hospital stay in days,
- e. Mortality (%) of overall and between groups,
- f. Pulmonary function
  - a. Time (days) to mechanical ventilation and/or
  - b. ECMO Duration (days) or extracorporeal membrane oxygenation (ECMO) use,
- g. SOFA score change from baseline to Day 9 and
- h. SOFA Respiratory sub-score change from baseline to Day 9,
- i. Number of venous thromboembolisms from admission to hospital discharge,
- j. Number of major bleeding events from admission to hospital discharge

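### A single signed change in fibrinogen cannot tell a fall from a high level from a fall below 100 mg/dL, and the protocol treats both ends of the range as abnormal

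*Combined protocol and SAP*

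**What the plan says.** Section 7 lists the endpoint in a single clause: "The Secondary endpoints include change from baseline D-dimers, Fibrinogen & Prothrombin time". Appendix C item b makes it "Fibrinogen level change from baseline to Day 9 in mg/dL". Neither gives a direction of benefit, a target range or a responder rule. Section 9 does not supply one. It allows means with SD or medians with interquartile range, tests at p < 0.05 without stating sidedness, and compares the fastest with the slowest recoverers rather than the randomised arms. Its stated expectation is "We expect that AT3 will correlate with rate of recovery and/or with one or more of the secondary outcomes", with no sign.

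Two other places bear on what a fibrinogen change means:

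- **Section 2 (Background)** describes the COVID-19 coagulation profile by "elevated D-dimer levels, and hyperfibrinogenemia". It also reports that fibrinogen was associated with interleukin-6, and was higher in 94 patients than in 40 healthy controls.
- **Appendix A**, which defines the primary score, counts "abnormal fibrinogen <1.0 gram/L level (1 point". Fibrinogen of 100 mg/dL or more scores 0. Section 2 also describes a consumptive coagulopathy.

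**The concern.** On the Section 2 reading, a fall from a high level is recovery. On the Appendix A reading, a fall below 100 mg/dL is consumption. The endpoint puts both on one axis with one sign, so a between-group difference, or its absence, does not show which kind of movement produced it. In an open-label trial with no stated sign, the interpretation could be chosen after the result is seen. At stake is whether the fibrinogen result can be used as evidence about AT3 supplementation. The primary endpoint has a clear direction and is not directly affected.

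**Working it through.** The plan gives no effect size, SD or power for fibrinogen, so there is no figure to reproduce. Inputs from the documents are the endpoint definition (Section 7, Appendix C b), the 100 mg/dL cut (Appendix A) and 25 patients per arm (Section 4). All fibrinogen levels, effects and SDs below are assumptions.

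**Step 1. Same signed change, different meaning.** Let F(x) = 1 if x < 100 mg/dL and 0 otherwise, as in Appendix A.

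| Baseline to Day 9 (mg/dL) | Signed change | Change in F | Reading |
|---|---|---|---|
| 700 to 400 | −300 | 0 | away from the high state in Section 2 |
| 390 to 90 | −300 | +1 | worse by Appendix A |
| 90 to 390 | +300 | −1 | better by Appendix A |
| 400 to 700 | +300 | 0 | further into the high state in Section 2 |

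**Step 2. An arm-level illustration.**

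- Control: 25 patients go from 650 to 410, so the mean change is 410 − 650 = −240.
- AT3: 22 patients go from 650 to 400 (−250) and 3 go from 250 to 80 (−170). The mean change is (22 × −250 + 3 × −170)/25 = −6,010/25 = −240.4.
- The means differ by 0.4 mg/dL, and the medians are −240 and −250. Yet 3/25 = 12% of one arm has newly fallen below 100 mg/dL, against none in the other.
- Those three patients move the arm mean of the primary score's fibrinogen item by 3 × 1/25 = 0.12 points.

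The example is constructed. Mean baselines are 650 and (22 × 650 + 3 × 250)/25 = 602, so it includes a baseline imbalance. It shows that masking is possible, not that it is likely.

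**Step 3. Benefits that cancel, over a range.** Suppose treatment lowers fibrinogen by 200 in patients who start high (share q) and raises it by 200 in consumptive patients, with within-type SD 150, 25 per arm and two-sided 0.05. Then D = −200q + 200(1 − q), treated-arm SD = √(150² + 4q(1 − q) × 200²), SE = √((150² + SD²)/25), and power = Φ(|D|/SE − 1.96) + Φ(−|D|/SE − 1.96).

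| q | D | Treated-arm SD | Power |
|---|---|---|---|
| 1.0 | −200 | 150 | 0.997 |
| 0.9 | −160 | 192 | 0.907 |
| 0.8 | −120 | 219 | 0.617 |
| 0.7 | −80 | 237 | 0.297 |
| 0.5 | 0 | 250 | 0.05 |

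**Step 4. Where might q lie?** The documents give no rate of fibrinogen below 100 mg/dL. The nearest figure is the 183-patient series in Section 2: mortality 11.5%, with DIC in 71.4% of deaths and 0.6% of survivors. That gives 0.115 × 0.714 + 0.885 × 0.006 = 0.087, or about 2 patients in 25. DIC criteria can be met without the fibrinogen item, so this does not estimate the rate. It suggests only that consumptive patients would be a small minority, nearer the top of the table than the bottom.

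**Step 5. Prothrombin time.** Section 2 reports longer times in non-survivors, and Appendix A adds points for prolongation. Section 13 lists PT among the tests used to guard against over- and under-anticoagulation. Over-anticoagulation is itself a harm, so a longer time is adverse there too. The passages agree.

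**The case against.** The strongest reply is that the protocol does not contradict itself. High fibrinogen as procoagulant and very low fibrinogen as consumptive describe two ends of one scale. Consumption is also already tracked: the primary score contains the 100 mg/dL item, alongside platelets, PT and D-dimer, and is recorded on Days 1, 3, 5, 7, 9 and 11. A patient falling to 80 mg/dL gains a point there. And this is one secondary laboratory marker in a pilot.

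Most of that stands. It limits the point to the secondary endpoint and its severity to minor. It does not remove the point, because a two-ended scale is exactly what one signed change cannot summarise, and the primary score is silent on all movement above 100 mg/dL, the range Section 2 describes.

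Several stronger readings are tempting but unsupported:

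- **That prothrombin time has the same conflict.** A reader might infer this from the drug's anticoagulant action and Section 13, but no passage calls a longer time beneficial.
- **That Appendix A makes any larger fall a harm.** It does not: every value of 100 mg/dL or more scores 0, so falls of 250 and 100 from 650 are scored alike.
- **That the endpoint is a mean.** Appendix C names no summary statistic and Section 9 allows medians. A median change is still signed, so the problem remains.
- **That Section 9 makes any correlation a formal success criterion.** It states an expectation. The weakness is that the expectation has no sign.

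**Conclusion.** The point holds for fibrinogen only, and it is minor. As defined, the endpoint cannot separate a fall from a high level from a fall below 100 mg/dL, whether summarised by mean or median, and the plan does not say which movement counts as improvement. Step 1 needs only the Appendix A cut and ordinary subtraction. The size of the effect on a trial result is unknown: Steps 2 and 3 rest on assumed values, and if nearly all patients start with high fibrinogen the loss is small. It would go too far to call any fibrinogen result uninterpretable. The narrower conclusion is that the result could not be interpreted from the signed change alone.

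**What to change.** 1. **Section 7 and Appendix C b.** Report, for each of the two randomised arms with AT3 < 100%, a baseline-to-Day-9 shift table with categories below 100 mg/dL, 100 to the laboratory upper limit, and above the upper limit, plus a column for patients with no Day 9 value. Count a new value below 100 mg/dL as worsening, as in Appendix A. Count a fall toward normal as improvement only in patients above the upper limit at baseline. State before analysis how a rise out of the middle band is labelled, and record each site laboratory's upper limit, which the documents do not give.
2. **Section 9, arm comparison.** Compare Day 9 fibrinogen between those two arms with baseline fibrinogen as covariate. This handles baseline imbalance and uses the randomisation, but it is still a comparison of means and does not solve the two-ended problem. The shift table does that.
3. **Section 9, correlation.** State the expected sign of any AT3–fibrinogen correlation before analysis, and count only that sign as support.
4. **Prothrombin time (Appendix C c).** Add one sentence saying that longer is worse, as Section 2 and Appendix A already imply.

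The cost is a few sentences, one model and one table. Appendix B already schedules fibrinogen at Days 1, 3, 5, 7, 9 and 11, so no visit or sample is added. With 25 per arm the shift table will be mainly descriptive. The one thing given up is that a result in the opposite direction can no longer be claimed as support.
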